10 DATA COLLECTION AND QUALITY ASSURANCE

10.1 Data Collection Forms

Study staff (e.g., CRC, research assistant) will collect and obtain study data directly from the participants (via in-person interviews) as well as from the participant's medical records. The collection, transfer and storage of data will be conducted in compliance with HIPAA and structured to minimize risk of protected health information disclosure. All records related to a participant's research will be stored in locked filing cabinets or on computers protected with passwords. Furthermore, study staff will record data directly into data collection forms that are present in REDCap and all web-based information transmission is encrypted. We also will rely on UR Box to store electronic information, which is HIPAA compliant. The database servers are housed in secure institutional data center facilities at University of Rochester. Additionally, audio recordings of intervention sessions will monitor fidelity and assist with quality control review. These audio recordings will be labeled using de-identified numbers only and will be stored on secure University of Rochester servers and/or the CRC and PI's computers. We will also use an encrypted voice recorder to protect participants' protected health information. Access to these audio recordings will be password protected and audio recordings will be in accordance with local and federal guidelines. The protocol includes a list of the study survey measures (Table 3). During the RN and OT intervention sessions, the RN and OT may decide to skip certain questions/items to focus on issues that are most relevant to each participant. Consequently, study interventionists can, at their discretion, skip or not complete questions in these assessments that they feel are less relevant to the participants they are working with for the study intervention visits. For fields/questions we believe are critical to the study, we will make sure that they require a response in REDCap and cannot be skipped, such as Adverse Event assessments.

10.2 Quality Assurance

10.3.1 Training

To ensure appropriate human research knowledge, all study personnel with access to subject research data will have completed mandatory training in the protection of human research participants per guidelines issued by the U.S. Department of Health and Human Services, Office for Human Research Protections (<https://www.hhs.gov/ohrp/>) and per guidelines of University of Rochester Medical Center (URMC). Any additional personnel will complete this training before having access to the study databases. Consistent with University of Rochester Medical Center RSRB policy, all investigators and research staff will complete certification by the RSRB, which requires completion of a course that contains topics such as "History and Ethical Principles," "Privacy and Confidentiality," "Informed Consent," and "The Federal Regulations." This course provides a substantial resource to the investigators for understanding the ethics and regulations governing research with human subjects. Research staff also will be trained to assess, de-escalate, and activate appropriate levels of care for those experiencing emotional distress

10.3.2 Quality Control Committee

Not applicable.

10.3.3 Metrics

Audiotaping of intervention sessions will be routinely conducted for fidelity and quality control review. OT/RN adherence to the intervention also will be quantified. Additionally, the PI and CRC will regularly monitor the database to ensure that data are appropriately recorded and complete.

10.3.4 Protocol Deviations

Study staff must not deviate from the protocol, except to protect the life and physical well-being of a participant in an emergency. All deviations from the protocol, with the reason for the deviation and the date of occurrence, will be documented using the Protocol Deviation Tracking Log Form. Protocol deviations will be reviewed and evaluated on an ongoing basis and, as necessary, appropriate corrective and preventive actions will be instituted.

10.3.5 Monitoring

The principal investigator will be responsible for monitoring the study. Routine monitoring will occur to verify that:

- participant enrollment is being achieved
- the inclusion/exclusion criteria has been met at enrollment
- the correct version of the informed consent has been signed by the subject
- AEs and SAEs have been captured and properly reported
- verify that the data are accurate and complete

11 PARTICIPANT RIGHTS AND CONFIDENTIALITY

11.1 Institutional Review Board (IRB) Review

The University of Rochester Medical Center's RSRB will review and approve this study's protocol and its informed consent document and any subsequent modifications.

11.2 Informed Consent Forms

We will obtain signed consent forms from each participant. As many of our participants may have cognitive impairment that could affect their ability to provide informed consent, we will systematically evaluate their capacity for informed consent. To do so, the CRC or research assistant will read the consent form to participants, who will be encouraged to ask questions throughout the process. To determine capacity for informed consent, at the conclusion of the consent process and prior to signing the consent form, study staff will ask all participants the following questions:

- Could you please tell me what this study is about?
- What are the potential risks to you of participating in this study?
- What are the benefits for participating in this study?
- Do you understand that your participation in this study is voluntary and that you may stop at any time or not answer any questions that you feel uncomfortable answering?
- Do you have any questions about the interview?

If in answering these questions the participant is unable to demonstrate an understanding or appreciation of the issues, research staff and the participant will further review the consent form and repeat the pertinent questions. Participants who achieve a demonstrated understanding of the study will be determined to have capacity to provide informed consent. For those who do not, research staff will attempt to identify a legally authorized representative (LAR; see Section 7.3.1 for definition of LAR) who also will need to demonstrate capacity to provide informed consent prior to signing the informed consent document. If the older adult is unable to provide informed consent and does not have a LAR able to provide informed consent, we will thank them for their time with \$10 for completing the screening and procedures and inform them that they are not eligible for the study. Participants' answers are tracked on a Determination of Consent Capacity Form that is kept with the research record as documentation of the consent process. For participants/LARs unable to provide informed consent, however, we will document the reason for study ineligibility on the Determination of Consent Capacity Forms. On these forms, we will not include any personal identifiers, but rather will use a screening ID number to track completion of these forms for participants and, if applicable, LARs. For participants and LARs unable to provide informed consent and who are not enrolled in the study, the screening ID number will not be linked to any personal identifiers. For enrolled participants who thereby demonstrate and provide informed consent or who have an LAR that provides informed consent, however, we will link these screening ID numbers with an assigned study-specific ID number that can be linked to identifiers we are collecting for the study. We will not keep any identifiable information for older adults/LARs who do not or are unable to sign consent to participate in our study. Rather, we will only keep basic demographic information such as age, sex, and race and ethnicity to allow us to track those who do and do not participate in our study; those older than 89 will be grouped in a 90+ age category.

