screening process for the CHHA to help us identify participants that have dementia or cognitive impairment. However, we will not base our recruitment criteria or numbers based on this dementia category but will prioritize people with dementia. This information will help us determine the representativeness of our study sample and to examine whether there are subgroups that are unlikely to participate in the study (in which case, we made need to bolster recruitment efforts for certain subgroups).

- **Consent procedures:** As part of the consent process, study staff will systematically assess capacity for consent with a series of open-ended questions administered to the potential participant that follows explanation of the study (see Determination of Consent Capacity Form). These questions will address the participant's knowledge and understanding of the study's objectives, the voluntary nature of participation, ability to withdraw at any time, and possible risks and benefits of participation. For those unable to demonstrate capacity for consent, we will seek to obtain surrogate consent. Surrogate consent for dementia research is widely accepted by the general public,^{54, 55} and we will only enroll older adults with a surrogate consent if the older adult also assents to participate in the study and the surrogate consenter is able to demonstrate capacity for consent. We will not enroll any older adult who is unable to demonstrate capacity to provide informed consent if they do not have surrogate consent available. Although we will not enroll these older adults, we will compensate them with \$10 for completing the screening procedures.
- **Randomization:** Immediately following termination of the baseline assessment interview, study staff will randomly assign participants via a stratified random permuted block method.¹ Randomization will be stratified based on cognitive impairment status (moderate/severe cognitive impairment present: MMSE score ≤ 20 ; moderate/severe cognitive impairment absent: MMSE ≥ 21).^{44, 45, 86} Block randomization will then occur within each strata to ensure appropriate allocation to the treatment and CAU groupings. REDCap⁵⁶ will track the randomization groupings.

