interest to participate in the research study and agree to have a study staff member visit them to provide more information, the study RN and CRC will work together to schedule an in-person screening visit that is convenient to the potential participant. Consent only will be sought under circumstances that provide the prospective subject sufficient opportunity to consider whether to participate and that minimize the possibility of coercion or undue influence. The information that is given to the subject or representative shall be in language understandable to the subject. Potential study subjects will be given ample time to read and consider the consent form. All subjects will be reminded of the voluntary nature of study participation. Using the consent form to structure discussion, research personnel will explain the study, its potential benefits and risks, and alternatives, and document the consent process by signature of the subject and the person obtaining consent. During informed consent procedures, individuals will be told about possible risks and benefits of participation. This will include information that questions asked may cause them to feel uncomfortable or upset. Subjects will be informed that they may withdraw from an assessment at any time for any reason and receive full reimbursement for that assessment, and that they may withdraw from the research study at any time without negative consequences. Subjects are further informed that research staff will perform an immediate evaluation of their safety should safety concerns arise during assessments or intervention sessions. For non-acute medical or psychological concerns research staff identify, we will recommend that subjects follow-up with their primary care physicians. Research staff will assess the subject's capacity with an RSRB-approved Determination of Consent Capacity Form that has been successfully implemented in other studies of older adults and consists of open-ended questions that will address the potential subject's knowledge and understanding of the study's objectives, general procedures, voluntary nature of participation (ability to withdraw), and possible risks and benefits of participation. For individuals who have difficulty in one or more of these areas, further review of the relevant elements of the study will be provided in order to improve their knowledge and understanding to a level that enables them to make a meaningful choice about participation. Those who demonstrate adequate capacity to consent will be invited to sign the informed consent form to enroll as a research subject. The consent will be an ongoing process during the study. Explanations of the study and verbal consent will be conducted at each data collection. Subjects will be reminded that their participation is voluntary and that they can withdraw at any time for any reasons.

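### The capacity questions in section 11.2 check voluntariness and withdrawal with a closed prompt and include no item on procedures, unlike the open-ended test described in sections 4.3 and 7.3.1

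*Combined protocol and SAP*

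**What the plan says.** Three places in the protocol describe the capacity assessment.

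- Section 4.3 (consent procedures) states that "study staff will systematically assess capacity for consent with a series of open-ended questions administered to the potential participant". The topics it lists are the study's objectives and "the voluntary nature of participation, ability to withdraw at any time, and possible risks and benefits of participation". Procedures are not on that list.
- Section 7.3.1 says the Determination of Consent Capacity Form consists of "open-ended questions that will address the potential subject's knowledge and understanding of the study's objectives, general procedures, voluntary nature of participation", and that it also covers withdrawal, risks and benefits.
- Section 11.2 gives the actual list: "prior to signing the consent form, study staff will ask all participants the following questions". There are five. Three are open: what the study is about, its potential risks, and its benefits. The fourth begins "Do you understand that your participation in this study is voluntary and that you may stop at any time" and goes on to the right to leave questions unanswered. The fifth is "Do you have any questions about the interview".

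Section 11.2 then sets the decision rule: "Participants who achieve a demonstrated understanding of the study will be determined to have capacity to provide informed consent". If understanding is not shown, staff go over the consent form again and repeat the relevant questions. If it is still not shown, they look for a legally authorized representative. Section 6.2.4 repeats the capacity determination at 3 and 6 months.

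**The concern.** The answers to these questions decide whether a person consents alone or enrols only with their own assent plus a representative's consent. The protocol relies on them heavily. Consent comes before the MMSE (section 6.2.2), so the cognitive score does not screen who is asked. People scoring 20 or less form a randomization stratum, and recruitment of people with dementia is prioritised (sections 6.2.2 and 9.2.1). Impaired participants may live alone (sections 2.2 and 5.2), and a study partner is optional (section 4.1).

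The two weakly covered topics are important ones here. Participants choose how much of the intervention to receive and are asked after each OT or RN visit whether to continue (section 5.1), so knowing that one may stop is central to the design. Taking part involves random assignment, up to 11 OT and RN home visits, possible alterations to the home, audio recording of sessions and extraction of medical records. If 11.2 is followed as written, someone can be recorded as capable without having been asked to explain either topic.

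**Working it through.** The protocol gives no figure to reproduce and none is needed. The check compares the 11.2 list with the topics and format stated in 7.3.1 and 4.3.

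| Topic | In 4.3 | In 7.3.1 | Item in 11.2 | Format in 11.2 |
|---|---|---|---|---|
| Objectives | yes | yes | what the study is about | open |
| General procedures | no | yes | none dedicated | – |
| Voluntariness and withdrawal | yes | yes | one shared item | closed |
| Risks | yes | yes | potential risks | open |
| Benefits | yes | yes | benefits | open |

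1. Against the five topics in 7.3.1, 3 of 5 have an open item (objectives, risks, benefits), 1 of 5 has a closed item (voluntariness with withdrawal) and 1 of 5 has no dedicated item (procedures). So 5 − 3 = 2 topics are not tested in the way 7.3.1 describes.
2. Section 4.3 names voluntariness and withdrawal separately, so its list also has five topics: objectives, voluntariness, withdrawal, risks and benefits. Three have an open item, and the other two share the single closed one. The gap on procedures therefore conflicts with 7.3.1 only. The closed format conflicts with both sections.
3. The fifth item in 11.2 maps to no topic. It invites questions, tests no content, and refers to an interview rather than the study.
4. The decision rule asks for understanding of the study as a whole. It gives no score, threshold or requirement for each topic. Section 7.3.1 comes closest, since it calls for further review when a person has difficulty in any one area. But difficulty with voluntariness or withdrawal is hard to see in a yes/no answer, and difficulty with procedures may not show when nobody asks about them.
5. The remedy in 11.2 is to repeat the relevant questions. For voluntariness and withdrawal, that means putting the same closed prompt again.

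A person who answers the three open items adequately and says yes to the fourth can therefore meet 11.2 as written without having stated in their own words that they may stop or what they will be asked to do.

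**The case against.** The strongest reply is that this is a mismatch of wording inside a sound process. Three of the five items cannot be answered by agreeing. Section 11.2 requires demonstrated understanding, with review and re-questioning before anyone is accepted and a search for a representative otherwise. Section 7.3.1 treats consent as continuing, with explanations, verbal consent and reminders of voluntariness at each data collection. Intervention participants are asked after each OT or RN visit whether they want to go on. Capacity is checked again at 3 and 6 months. An open question on what the study is about may draw out procedures unprompted. The Determination of Consent Capacity Form is described as RSRB-approved and used successfully in other studies of older adults. It is not in the documents and may hold better prompts than the list in 11.2. The trial is described as minimal risk.

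Much of this stands. A reader might infer that people can pass the capacity test simply by agreeing and so bypass the representative. The documents do not support that: a bare yes to one item does not establish capacity. A reader might also infer that enrolment or self-consent in the impaired stratum is overstated as a feasibility result. That is not supported either. Self-consent is not a listed outcome, no stratum-specific enrolment outcome is defined, and a person found to lack capacity may still enrol by assent with a representative. The documents give no basis for putting a rate on wrong determinations.

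The reply does not remove the mismatch itself. Reminding people that they may stop is not the same as asking them to show that they know it. The 3- and 6-month checks help only if their items differ from the list in 11.2, and the protocol does not say that they do.

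**Conclusion.** The point holds in a limited form. Section 11.2 contradicts 4.3 and 7.3.1 on the format of the voluntariness and withdrawal item, and contradicts 7.3.1 on coverage of procedures. Two of the five topics in 7.3.1 are not tested as described. With no requirement set for each topic, a person could be judged capable without showing in their own words that they understand voluntariness, withdrawal or procedures.

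This is a question of participant protection and of consistency within the protocol. It does not touch the sample size or the planned analyses. It is worth correcting because the trial deliberately enrols people with moderate or severe cognitive impairment and the correction is small.

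The conclusion assumes that staff ask the items as printed in 11.2. If the form already contains open items on both topics, only the text of 11.2 and the list in 4.3 need changing.

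**What to change.** In section 11.2, and in the Determination of Consent Capacity Form if it uses the same wording:

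- replace the closed item on voluntariness and withdrawal with an open one, for example *What can you do if you no longer want to take part?*;
- add an open item on procedures, for example *What will you be asked to do in this study?*;
- refer to the study, not the interview, in the last item;
- say what counts as demonstrated understanding for each topic;
- add general procedures to the list in 4.3 so that it agrees with 7.3.1;
- state that the same items are used at baseline, 3 and 6 months.

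The cost is ethics-board approval of a short change to the protocol and form, and a minute or two per participant at each assessment. The downside is that a few more people may need a representative, which could slightly slow enrolment among those with cognitive impairment.

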11.3 Participant Confidentiality

All participant data, including assessment measures, will be obtained with the written consent of the participant or surrogate decision-maker. All data collection will be HIPAA compliant, and a uniquely coded study number assigned to each participant will identify participant data (i.e., a participant ID number). To protect the confidentiality of participant information, we will take a number of precautions:

- use research personnel trained in confidentiality procedures
- enter and store data on highly secure servers
- maintain project computers in secure locations (e.g., locked offices)
- restrict access to study data to study personnel on a needed to know basis that is enforced with password protection
- minimal reliance on paper documents
- publications or presentations will report only cumulative data or descriptions certain to maintain participants' anonymity

In particular, we will rely on URMC's REDCap servers housed in a local data center at the University of Rochester (all web-based information transmission is encrypted). REDCap was developed in a manner consistent with HIPAA security requirements and is recommended to University of Rochester researchers by the URMC Research Privacy Officer and Office for Human Subject Protection. Access to computerized data is restricted and subject to review by the PI. In accordance with local and federal guidelines, we will keep study data for a minimum of three years following submissions of the final reports to NIA.

Furthermore, information pertaining to individual participants will be released with the participant's informed and written consent only, except in unusual cases where withholding the information might pose a serious risk or danger to the participant or others. If necessary, information also may be released without written permission of the participant for monitoring by the RSRB, NIA, OHRP, or other governmental agency.

11.4 Study Discontinuation

The study may be discontinued at any time by the RSRB, the NIA, the Office for Human Research Protections, or other government agencies as part of their duties to ensure that research participants are protected.

